7.2. Eligibility Criteria

The study population will be women with CF who have used any form of contraception for protection against pregnancy or for treatment of dysmenorrhea, pelvic pain, abnormally heavy or prolonged menstrual bleeding, excessive uterine bleeding, endometriosis, acne, or amenorrhea.

Table 4: Full study inclusion and exclusion criteria

Inclusion Criteria
Females ages ≥ 18 and < 46 years at enrollment
Confirmed patients at one of the 10 participating CF centers (has been seen at least one time for a face-to-face
office visit at the CF center in the last 2 years)
CFFPR participant (noted as having a CFFPR ID number)
Has internet access
Has a functioning email addresses or may create a functioning email address at enrollment
Willing to consent to obtain request of their identified data from CFFPR
Willing to consent to their CF center to provide data related to contraceptive medication and DXA scan test results
as far back as 2013 in clinic EMR
Exclusion Criteria
Not in CFFPR
Non-functioning email address
History of organ transplant
Participant in pre-test phase of this study

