6.2. Pilot Process: Please see Pilot Pre-test Survey Protocol for Details

We will not be able to validate responses against the EMR because of research suggesting that EMR data are not accurate with regards to contraceptive information (9).

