7.3. Interventions

We will provide an online questionnaire to give to female participants in order to obtain exposure data (past contraceptive use). We will have participants complete the survey on their own, either in clinic or at home. The survey will include pictures, brand names, and descriptions to help respondents remember birth control method used retrospectively.

We will ask each CF center to provide DXA scan results for 10 participants (selected at random) from their respective EMRs in order to validate osteoporosis, osteopenia and bone fracture information in the CFFPR.

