9.1.2. Clinic Case Report Forms (CRF)

We are requesting CRFs from each of the 10 CF centers in order to verify DXA scan findings with bone data reported in the CFFPR.

Table 9: Information sought on CRF

EMR Data Request

• DXA scan results: dates and results as far back as 2013. Results will include T-scores and Z-scores from 3 sites: femoral neck, lumbar spine, and total hip and date that DXA scan was performed.

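### Table 4 makes chart release a condition of entry, although no form or analysis uses the chart contraceptive records and DXA results are used for only about 100 women

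*Combined protocol and SAP*

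**What the plan says.** Table 4 (section 7.2) has two separate release criteria. One covers the registry: "Willing to consent to obtain request of their identified data from CFFPR". The other covers the clinic chart: "Willing to consent to their CF center to provide data related to contraceptive medication and DXA scan test results", reaching back to 2013. Both are conditions of entry, and the table shows no opt-out for either.

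What the centers are asked to extract is narrower. Section 7.3 says "We will ask each CF center to provide DXA scan results for 10 participants (selected at random". Section 9.1.2 says "We are requesting CRFs from each of the 10 CF centers in order to verify DXA scan findings with bone data reported in the CFFPR", and Table 9 lists "DXA scan results: dates and results as far back as 2013", with scores at three skeletal sites. Table 6 and steps 11 and 12 of section 7.6.2 also ask for DXA alone. None of them has a contraceptive field.

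Exposure comes from the participant. Section 7.3 says "We will provide an online questionnaire to give to female participants in order to obtain exposure data (past contraceptive use". The Summary (1.0) explains why: charts are often wrong about contraception and leave out over-the-counter methods. Section 6.2 makes a similar remark about the pilot, citing "research suggesting that EMR data are not accurate with regards to contraceptive information".

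The scope of the DXA work is stated in conflicting ways. Section 4.2 limits it to one center; sections 5.0, 7.3, 7.6.2 and 9.1.2 use all ten. Sections 5.0 and 7.3 sample from participants in general, while step 10 of section 7.6.2 samples only women whose registry record shows osteopenia or osteoporosis.

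**The concern.** The criterion asks every participant to release a type of record that the plan distrusts and never collects, and a second type that it will use for about one woman in six. Neither enters the primary analysis. A woman willing to complete the survey and have it linked to the registry, but not willing to open her chart, is ineligible for everything.

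The plan itself calls contraception, pregnancy and menstruation sensitive topics (1.0, 6.0). It invites all qualified women in order to limit selection (7.8), and it lets participants skip any survey question (10.2). A compulsory release of unused contraceptive records works against those aims. At stake are avoidable exclusions and possibly some selection, most plausibly for the self-reported unintended-pregnancy endpoint. It is also hard to justify to an ethics board a consent that has no stated use.

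**Working it through.** **1. The plan's own DXA count.** 10 women per center (7.3) × 10 centers = 100, which matches step 11 of section 7.6.2. As a share of enrollment: 100/625 = 16.0%, 100/600 = 16.7%, 100/575 = 17.4%. If the one-center statement in 4.2 governs, about 10 women are used: 10/625 = 1.6% to 10/575 = 1.7%.

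**2. What each part of the plan needs.**

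| Item | Source in the plan | Chart needed? |
|---|---|---|
| Contraceptive exposure | Online survey (7.3, 9.1, Table 10) | No |
| Exacerbations, FEV1 and other registry outcomes | CFFPR (1.0, Appendix) | No |
| Thromboembolism, pregnancy intention | Survey (Tables 5 and 10) | No |
| Validation of registry bone data | Center DXA form (7.3, Table 9) | Yes, DXA only |
| Chart contraceptive records | On no form, in no analysis in 9.3 | Requested in Table 4 only |

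So the contraceptive release feeds no analysis, and the DXA release feeds one secondary objective.

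**3. Recruitment margin.** The center table in 7.1 lists 141 + 140 + 233 + 120 + 106 + 128 + 159 + 135 + 189 + 51 = 1402 women. At the anticipated 50% uptake, 0.50 × 1402 = 701. The refusal share that brings 701 down to a target N is 1 − N/701:
- N = 575: 1 − 575/701 = 18.0%
- N = 600: 1 − 600/701 = 14.4%
- N = 625: 1 − 625/701 = 10.8%

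This assumes that refusals come on top of the 50%. If the 50% is already net of them, the targets are not threatened by refusal at all.

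**4. Slack at the smallest center.** It lists 51 women; 0.50 × 51 = 25.5, about 26 enrolled. Ten of these is 10/25.5 = 39%. Under step 10 of section 7.6.2, all ten must also carry a registry bone diagnosis.

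**The case against.** **DXA release has a purpose.** A reader might infer that the whole criterion serves nothing. The documents do not support that. Validating registry bone data is a stated secondary objective, and the women are drawn after enrollment, so nobody knows at consent who will be chosen. Consent from everyone enrolled gives a sampling frame with no further opt-in among them. That stands. However, women who refuse chart release are already missing from the frame under the compulsory rule, because they are not enrolled. The only new loss under an optional item is women who would agree if required but decline if asked.

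**Power.** A reader might also infer a material loss of power. Table 8 implies (z for power + 1.96)²/n of about 0.0163 per woman, so with the stated 15% attrition, power = Φ(√(0.0163 × 0.85 × N) − 1.96). For N = 575 this gives 0.81. If 5%, 10% or 15% of 575 were lost (N = 546, 518, 489), it gives 0.79, 0.76 or 0.74. Those refusal rates are assumptions with no source in the documents. The calculation treats 575 as the number before loss, although the plan expects about 600 and recruits up to 625. The last two cases also leave 440 and 416 women after attrition, below Table 8's lowest row of 450. Recruiting to a target would replace the women lost.

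**Bias in the primary result.** Selection related to contraceptive use alone does not bias the exacerbation rate ratio; refusal would also have to be related to exacerbations, and nothing in the documents shows that. A link to the pregnancy endpoint is plausible but unmeasured. The group may be small, since these women would already have agreed to survey questions on pregnancy and to identified registry data.

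**Limits of the evidence.** The consent pages are not available, so a tiered consent form cannot be ruled out; Table 4 as written shows none. The remark in 6.2 concerns the pilot, and the Summary is the stronger source on chart quality.

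**Conclusion.** The mismatch is certain from the documents and needs no outside figure. Release of chart contraceptive records is required of every participant and used nowhere. DXA release is required of every participant and used for about 100 women, 16% to 17% of enrollment, or under 2% if 4.2 governs. A woman who accepts the survey and registry link but declines chart release is excluded from the primary analysis without need.

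The effect is not known. The documents give no refusal rate, so neither the number excluded nor any selection can be sized. A power loss is not shown: on the planned uptake, refusal would have to reach about 18% before enrollment fell below 575. The point is worth correcting because the exclusion is avoidable and the correction is cheap, not because the primary result is shown to be at risk.

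**What to change.** - Delete contraceptive medication from the Table 4 criterion. This has no downside under the current plan. If the sponsor does intend a use for those records, the plan should state it and add the field to the center form.
- Make DXA chart release a separate consent item that is not a condition of entry.
- Draw the DXA sample from women who agree, and report the share agreeing by center.
- Reconcile 4.2 (one center) with 5.0, 7.3, 7.6.2 and 9.1.2 (ten centers). State one sampling frame: all consented women, or those with a registry diagnosis of osteopenia or osteoporosis. Settle this before rewording the consent.

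Cost: wording changes to Table 4 and the consent form, with an IRB modification; no new data and no extra staff. The downside is that some women who would agree if required may decline if it is optional. That makes the DXA sample somewhat more self-selected and may leave fewer than 10 at the smallest center, so the plan should allow a smaller number there.

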4.0. Study Objectives

4.1. Primary Study Objective

• To assess the association of hormonal contraceptive use on frequency of pulmonary exacerbations, compared to non-hormonal contraceptive users (primary control) and non-contraceptive users (secondary control).

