7.0. Methods: Participants, Interventions, and Outcomes of Final Questionnaire Phase

Once the questionnaire is pretested (anticipated end date of pre-testing is July 2020), the final questionnaire will be revised accordingly prior to initiating the full, larger study.

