7.1.1. Study Duration

Participant enrollment will take approximately 15 months for the finalized survey phase.

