7.2.2. Enrollment

The participant is considered enrolled into the study after providing written consent and is found eligible based on history, eligibility screening questions, and confirmation as a participant in the CFFPR. Eligible consented participants who withdraw consent for any reason before completing the survey are considered screen failures. Eligible consented participants who cannot be verified as a participant in the CFFPR with a CFFPR ID number (confirmed by respective CF center) will be considered a screen failure.

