9.3. Statistical Methods

Because this is a retrospective cohort study, we are most interested in determining whether this exposure (to hormonal contraception) is associated with our primary outcome (counting the number of pulmonary exacerbations requiring additional IV in a given year) and/or our secondary outcomes (new respiratory microbiology, liver disease/non-cirrhosis, gallstone, requiring surgery/procedure, improved BMI, incidence of VTE, osteoporosis and fragile bone fracture). Women on hormonal contraception will be compared to the primary control group of women on non-hormonal contraception. We will also compare to women on no contraception, as the secondary control group. We will exclude persons with these existing diagnosis at the start of the follow up period for outcome data (January 1, 2010). Within this objective we will be able to calculate incidence rates, relative risks and confidence intervals. We will use Poisson regression to calculate progestin-only and combined hormonal method to non-hormonal method pulmonary exacerbation rate ratios and 95% confidence intervals. This allows for adjustment of follow-up time of each individual.

(Objective 1a): We will evaluate lab values over time (ppFEV1%, serum AST, ALT, alkaline phosphatase) to determine if trends between hormonal contraceptive users and non-hormonal contraceptive users differ. See Table 5 for confounders and covariates that we will use to adjust for the primary and secondary outcomes.

We will model ppFEV1 via generalized estimating equations (GEE), allowing for correlation within a subject, and compare via a fixed effect for exposure. Among women who change or stop contraception, we will estimate and compare within-participant difference in outcomes via the model (if numbers allow). We will censor women who switch method types or become pregnant, and for 6 months post pregnancy, for the primary analysis and subsequently follow them to leverage within-patient data and analyze changes in pulmonary status and contraception. Presence of respiratory microbiology will be estimated longitudinally via GEE with a logit link function. Graphic displays and summary statistics will be used; all *p* values will be two-sided.

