10.4. Duration of Project (see Table 11)

- The duration of the project is expected to be about 36 months.
- Recruitment is expected to take 12 months.
- Merging of the data and cleaning the database is expected to take up to 4 months.
- Data analysis will take 3 months.
- Creation of the web-based REDCap database for data entry will occur before enrollment begins, and data entry will be ongoing throughout the study.

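### The undated transplant exclusion is applied at enrollment, so a woman transplanted after 1 January 2010 loses all her valid pre-transplant follow-up

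*Combined protocol and SAP*

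**What the plan says.** Section 7.2, Table 4, lists "History of organ transplant" as an exclusion, with no date, organ or rationale. Under section 7.2.2 a woman is enrolled once she has consented and "is found eligible based on history, eligibility screening questions, and confirmation as a participant in the CFFPR", so the criterion looks back from the day of enrollment. In section 7.6.2 the screening questions come before consent, so an excluded woman never consents to registry linkage.

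For the calendar, section 7.0 gives "anticipated end date of pre-testing is July 2020". Section 7.1.1 says "Participant enrollment will take approximately 15 months for the finalized survey phase", and section 10.4 says "Recruitment is expected to take 12 months".

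Section 9.3 handles existing outcome diagnoses differently: "We will exclude persons with these existing diagnosis at the start of the follow up period for outcome data (January 1, 2010"). That exclusion is fixed at the start of follow-up.

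The primary objective in section 4.1 is "To assess the association of hormonal contraceptive use on frequency of pulmonary exacerbations". Secondary objectives in section 4.2 include FEV1 trend and liver dysfunction. Cirrhosis is named as an endpoint there only; Table 5 and section 9.3 name non-cirrhotic liver disease instead.

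**The concern.** In a retrospective cohort, eligibility should depend on what was true when follow-up began. Here it also depends on something that may have happened up to a decade later. Lung or liver transplant is plausibly the end of a severe course on the same scales that the study measures. A woman with frequent IV-treated exacerbations and falling FEV1 from 2010 to 2016 and a transplant in 2017 has seven full, valid outcome years, and the plan discards them all.

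Two things are at stake. Exacerbation rates in the remaining women would tend to be too low in every group. The contrast between hormonal and non-hormonal users would also be distorted if transplant is more frequent in one of them.

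**Working it through.** **1. Dates side by side**

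| Item | Source | Date |
|---|---|---|
| Outcome follow-up starts | 9.3 | 1 January 2010 |
| Registry data end | 5.0 | 2018 or 2019 |
| Registry data end, other statements | 11.0, Appendix | open: most recent year available |
| Enrollment starts, at the earliest | 7.0 | about August 2020 |
| Enrollment ends, 12 months | 10.4 | about mid-2021 |
| Enrollment ends, 15 months | 7.1.1 | about late 2021 |

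The criterion is therefore applied at least ten and a half years after follow-up starts. Under section 5.0 it is also applied after follow-up ends.

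**2. Does anything in the plan offset it?**

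- Censoring in section 9.3 covers method switch and pregnancy only.
- The two sensitivity analyses concern women from the prior study (7.1) and missing data (9.3).
- The surgical history in Table 10 covers operations that prevent pregnancy.
- The Appendix requests no transplant status or date.

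As planned, the loss can be neither corrected nor measured.

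**3. Direction and size, by a two-class illustration**

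The plan states no figure to reproduce. From section 7.7 I take a control rate of 0.8 per year and a rate ratio (RR) of 0.70 as the truth. Assumptions: a share q0 of controls and q1 = k × q0 of hormonal users are transplanted by enrollment, and in both groups these women have m times the exacerbation rate of the rest. After they are removed:

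- control rate = 0.8 / [1 + q0(m − 1)]
- observed RR = 0.70 × [1 + q0(m − 1)] / [1 + q1(m − 1)]

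For q0 = 5%, m = 3, k = 0.7, so q1 = 3.5%: control rate = 0.8 / 1.10 = 0.727, and RR = 0.70 × 1.10 / 1.07 = 0.720.

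| q0 | m | Control rate | RR, k = 1 | RR, k = 0.7 | RR, k = 0.5 |
|---|---|---|---|---|---|
| 2% | 2 | 0.784 | 0.700 | 0.704 | 0.707 |
| 5% | 3 | 0.727 | 0.700 | 0.720 | 0.733 |
| 10% | 4 | 0.615 | 0.700 | 0.752 | 0.791 |

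With equal transplant frequency (k = 1) the RR does not move, but the control rate still falls. If transplant is more common in users, say k = 1.5 with q0 = 5% and m = 3, the RR is 0.70 × 1.10 / 1.15 = 0.670, so the shift reverses.

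**4. Size when transplant risk follows a woman's own rate**

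A simulation assumed gamma-distributed rates (means 0.8 and 0.56 per year, variance factor 1 or 2), 9 years of follow-up, and an annual transplant hazard of 0.003 × (rate/0.8)^1.5. Then 3 to 4% of controls are transplanted, and fewer hormonal users, because their rates are lower. Excluding transplanted women gives an RR of about 0.72 to 0.73 and a control rate of 0.72 to 0.76. Censoring at transplant instead recovers at most about half of the RR shift.

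**The case against.** **Excluding post-transplant time is reasonable.** Exacerbations and FEV1 no longer measure the same thing after a lung transplant. This stands, but censoring at the transplant date achieves it without deleting earlier years. Transplants before 2010 are an ordinary baseline exclusion and are not at issue.

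**Transplant is not an endpoint.** A reader might infer that women are removed because of their outcome. The documents do not support that: no objective or outcome table lists transplant, and the criterion covers any organ. The link to severity is an inference. For the liver it also depends on which section governs, since cirrhosis is an endpoint only in section 4.2.

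**The severe cases are not all lost.** A reader might infer that severe lung and liver outcomes are removed by design. Only transplanted women are removed. Women with many IV-treated exacerbations, low FEV1 or cirrhosis but no transplant remain.

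**The timing is less clean than it looks.** Enrollment falls wholly after the outcome years under section 5.0. The open-ended data request in section 11.0 and the Appendix could let the two overlap. The selection remains either way.

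**The effect may be small next to sampling error.** This stands. Take 575 × 0.85 ≈ 488 evaluable women, split equally, with 9 years each and variance factor 1. The variance of log RR is [1/(0.8 × 9) + 1]/244 + [1/(0.56 × 9) + 1]/244 = 0.0096, so the standard error is 0.098 and the 95% interval around 0.70 is about 0.58 to 0.85. A shift to 0.73 is ln(0.73/0.70) = 0.042, under half a standard error. The illustrations also ignore the covariates in Table 5, which could absorb some of the variation between women.

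**Conclusion.** The timing defect is in the text. An exclusion judged in 2020 or 2021 deletes valid person-time that began in 2010, on the basis of a later event that is plausibly related to severity, and nothing in the plan offsets it.

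Absolute exacerbation rates are likely understated. If transplanted women stand out from the rest by the same factor in each group, the rate ratio is biased only when transplant frequency differs by exposure. The shift is toward 1 if hormonal use is protective, as section 3.0 hypothesises for estrogen-containing methods. A reader might take bias toward 1 as certain. It is not: transplant could be equally common in the groups or more common in users, and the documents give no rate, overall or by exposure.

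The size is therefore unknown. With 3 to 4% of controls transplanted, under the assumed hazard and variation, 0.70 becomes about 0.72 to 0.73. The larger shifts, up to 0.79, need transplant shares of 10% or more that nothing in the documents supports, and they should carry no weight. The case for change rests on a clear and avoidable selection, not on a proven large bias.

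**What to change.** - **Table 4:** limit the exclusion to organ transplant before the start of outcome follow-up (1 January 2010).
- **Section 9.3:** add first organ transplant, with its date, to the censoring events.
- **Table 10 and Appendix:** add transplant status and date to the survey and to the registry (CFFPR) variable request.

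The cost is one eligibility line, one censoring rule, one survey item and one registry variable. The cap of 625 is unchanged. The change has to be made before screening, because women screened out do not go on to consent and their data cannot be recovered at analysis.

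The correction is partial, and the plan should state this as a limitation. Censoring at transplant is itself related to severity. Women who died before enrollment are still missed. Transplanted women must also still meet the Table 4 requirement of a face-to-face CF-center visit in the last 2 years.

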7.2.1. Informed Consent

By obtaining informed consent from participants, the UW study team shall:

- Avoid any coercion of or undue influence to participate
- Sustain the candidate's legal rights
- Provide complete, detailed description of study, intent to link survey information with participant's clinical information in the CFFPR, follow up and costs/reimbursements using language that is non-technical and understandable to the participant
- Ensure the participant understands the risks and responsibilities
- Include contact information of the principal investigator and study site investigator
- Ensure protection of the participant's confidentiality

